TITLE: Strength Training and Endurance Exercise for LIFE

Trial # NCT02102060
Registered 3/27/2014

Principal Investigators

[name], ScM,^{1,2}
[name]^{3,4}

1 Salem Veterans Affairs Medical Center, Salem, Virginia

2 Virginia Tech Carilion School of Medicine, Roanoke, Virginia

3 Baltimore Veterans Affairs Medical Center Geriatric Research, Education, and Clinical Center at the Veterans Affairs Maryland Health Care System

4 University of Maryland School of Medicine, Baltimore, Maryland

Funding

The research described here was supported by the Department of Veterans Affairs Veterans Health Administration, Rehabilitation Research and Development Service, I01 RX000667

Ethics approval and consent to participate

The study was approved by the Institutional Review Boards at the Salem VAMC, Salem, VA and the University of Maryland IRB, Baltimore, MD.

Written informed consent was obtained from each patient prior to participation.

Protocol Overview

Hypothesis: We hypothesize that high-intensity exercise training will increase cardiorespiratory fitness, which will be mediated by improved diastolic function and will correlate with decreased biomarkers of inflammation.

Background: Adults with HIV on antiretroviral therapy have a life expectancy approaching that of the general population yet have impaired cardiorespiratory fitness and diastolic function that increase their risk for age-related disability. Chronic inflammation is a well-studied mediator of advanced aging with HIV, including cardiac dysfunction, yet the impact of exercise training is unclear. The study objective is to develop an exercise program for older adults with HIV that targets pathophysiological processes of advanced aging and will prevent and improve disability.

Design: The study is a randomized trial comparing 16-weeks of progressive aerobic and resistance training to usual care in sedentary older (50+ years) adults with HIV. The center-based exercise training is performed three times weekly under supervision. The end-target duration and intensity of aerobic exercise is 45 minutes at 70-80% of baseline heart rate reserve. Resistance training progresses from low-intensity to high-intensity based on initial one repetition maximum (1-RM) in the three upper body (chest press, seated row, pull-down) and three lower body exercises (leg press, knee extension, knee flexion). Primary outcomes are cardiorespiratory fitness, cardiac function, and biomarkers of myocardial fibrosis and cardiac stress. Secondary outcomes include muscle strength, body composition measured by Dual-energy X-ray absorptiometry (DXA), and biomarkers of systemic Inflammation.

Statistical Analysis Plan (SAP)

Power Analyses

Power calculations were based on results from randomized exercise trials that included a sedentary control group. For outcomes of diastolic function¹, cytokines², and biomarkers of myocardial fibrosis³ we used mean (SD) from exercise trials in older adults without HIV since results were not available for adults with HIV. Referenced values for VO₂peak⁴ and strength⁵ were obtained from trials in adults with HIV, but a younger population (mean age 30-45 years old). For these outcomes, a sample size of 22 participants per group provides at least 80% power to detect a between group difference with a two-sided alpha of 0.05. We acknowledge that older participants may have greater muscle soreness or fatigue as well as more medical problems. Therefore, our target enrollment number assumes a conservative attrition rate of 30% based on prior exercise interventions in adults with HIV.^{6,7}

Statistical Analyses

ANOVA will be used to compare the change in the intervention group to the change in the control group for the following primary outcomes, AIM 1: (1) functional performance, (2) aerobic capacity, (3) diastolic function; AIM 2: (1) strength, (2) muscle mass. In the ANOVA models, the change from baseline to 16-weeks will be the dependent variable in models adjusted for the baseline value of the outcome measure and treatment group. Groups will be compared at baseline for differences in potential confounders such as age and comorbidity. Additional adjustment will be made if the randomization produces groups that are not balanced on factors which are also associated with outcomes. We do not anticipate needing to adjust for sex, history of AIDS, or length of HIV infection (CD4 cell count) as our group assignment will be blocked on these factors. Similar analyses will be performed for secondary outcomes, intramuscular fat,

percent body fat, plasma glucose, insulin, and lipids, blood pressure. All analyses will be two-tailed.

We will use regression analyses to test the following associations, Specific aim 1: change (16-week value minus baseline value) in VO₂peak with change in (1) diastolic function and (2) markers of systemic chronic inflammation, (3) change in diastolic function with change in myocardial fibrosis; Specific Aim 2 (1) change in strength with change in muscle mass, (2) change in muscle mass with change in markers of inflammation, change in intramuscular fat with change in (3) plasma lipid and (4) fasting glucose concentrations. These analyses will be adjusted as noted above, except they will not be adjusted for group as the analytic interest lies in the relation of change to change, not change to group.

Analyses will include subjects who drop out before completion of the 16-week study period by way of multiple imputation. This intention to treat approach will investigate factors that may affect compliance and difficulty with exercise training, including pain/soreness and medical comorbidity. If the pattern of missing data is missing completely at random, or simply at random, our multiple imputation should eliminate bias due to loss to follow-up. Because the majority of the subjects will be recruited from the Salem VA HIV clinic, we will be able to obtain clinical data from subjects who drop out of the study, but remain in clinical care, to determine if drop-out was related to medical conditions that may influence outcomes. Thus, we will be able to estimate bias introduced by loss to follow-up. If there is sufficient information, we may be able to model the drop-out process and adjust our analyses for loss to follow-up even if the missing data pattern is non-ignorable. If 48 training sessions cannot be completed in 16 weeks, then total training time will be tracked, and incorporated into the data analysis.

Data management

A robust data management plan is in place to ensure the accuracy, completeness, legibility, and timeliness of the data collected across the two sites. The study data is managed carefully to ensure its integrity. Ongoing quality assurance activities include summary statistics to identify outliers that are then confirmed with source documents. To maintain participant confidentiality, each participant is assigned a numerical ID which is used on all case report forms, data sheets and surveys. The keycode to link individuals with their assigned IDs are stored in locked cabinets and computer folders separate from study data. Data is entered directly from the source documents into data spreadsheets that are stored in limited access study folders on the VA server that can be accessed only through a password protected VA computer from either site.

REFERENCES

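### The Design and Statistical Analyses sections name different primary outcomes, and the fibrosis and cardiac-stress biomarkers that the Design calls primary have no between-group test

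*Combined protocol and SAP*

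**What the plan says.** Outcome tiers appear in two places. The Design paragraph of the Protocol Overview says "Primary outcomes are cardiorespiratory fitness, cardiac function, and biomarkers of myocardial fibrosis and cardiac stress", and then "Secondary outcomes include muscle strength, body composition measured by Dual-energy X-ray absorptiometry (DXA), and biomarkers of systemic Inflammation".

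The Statistical Analyses section specifies an ANOVA on change from baseline to 16 weeks, adjusted for the baseline value, with treatment group in the model. It applies this to "the following primary outcomes, AIM 1: (1) functional performance, (2) aerobic capacity, (3) diastolic function; AIM 2: (1) strength, (2) muscle mass". It then extends the method: "Similar analyses will be performed for secondary outcomes, intramuscular fat", followed by "percent body fat, plasma glucose, insulin, and lipids, blood pressure". No other between-group analysis is described.

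Fibrosis appears in that section once, as an item in the Aim 1 regressions: "3) change in diastolic function with change in myocardial fibrosis". The same paragraph says these regressions leave out treatment group, because the interest is in how one change relates to another.

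Power Analyses names diastolic function, cytokines, fibrosis biomarkers, VO₂peak and strength. For the first three the inputs came from other populations ("and biomarkers of myocardial fibrosis³ we used mean (SD) from exercise trials in older adults without HIV"). It concludes: "For these outcomes, a sample size of 22 participants per group provides at least 80% power to detect a between group difference".

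**The concern.** The two lists cannot both be the trial's primary outcomes, and the document gives no rule for choosing between them. It states no hierarchy and no multiplicity rule, so either list could later be presented as the primary set.

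The second problem is an omission. An analyst who followed Statistical Analyses exactly would never compare the randomised groups on fibrosis or cardiac-stress biomarkers, both primary in the Design. The one analysis that uses fibrosis does not estimate what training does to it.

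**Working it through.** **The plan's own figure.** The 22 per group cannot be reproduced, because no difference or SD is printed for any outcome. It can only be inverted. With 80% power and two-sided alpha 0.05, d = (1.960 + 0.842) × √(2/22) = 0.845 under the normal approximation (0.865 for a t test). The finding does not depend on this figure. What matters is that the power claim concerns a between-group difference and includes fibrosis.

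**The sections side by side.**

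| Outcome | Design | Statistical Analyses | Between-group test | In Power Analyses |
|---|---|---|---|---|
| Fitness / aerobic capacity | primary | primary, Aim 1 | yes | yes (VO₂peak) |
| Cardiac / diastolic function | primary | primary, Aim 1 | yes (diastolic) | yes (diastolic) |
| Fibrosis biomarkers | primary | no tier; regression only | **no** | yes |
| Cardiac-stress biomarkers | primary | absent | **no** | no |
| Functional performance | absent | primary, Aim 1 | yes | no |
| Strength | secondary | primary, Aim 2 | yes | yes |
| Muscle mass | secondary, if it is the DXA measure | primary, Aim 2 | yes | no |
| Inflammation biomarkers | secondary | no tier; regressions only | **no** | yes (cytokines) |

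The secondary outcomes that get a between-group test are intramuscular fat, percent body fat, glucose, insulin, lipids and blood pressure. None is a fibrosis, cardiac-stress or inflammation biomarker.

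**Counts.** The number called primary in at least one section is the Design count plus the Statistical Analyses count, minus the overlap. Cardiac function is read as diastolic function, so the overlap is 2.

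- All aims: 4 + 5 − 2 = 7 outcomes, 2 in both.
- Aim 1 only: 4 + 3 − 2 = 5 outcomes, 2 in both.
- Two biomarker groups counted as one item: 3 + 5 − 2 = 6 for all aims and 3 + 3 − 2 = 4 for Aim 1, with 2 in both.
- Cardiac function not equated with diastolic function: the overlap falls to 1.
- Design primaries without a between-group test: 2 of 4 (1 of 3 if the biomarkers are one item).

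**Why the regression cannot stand in for the missing test.** Let δF and δD be the effects of training on the changes in fibrosis and diastolic function, and let c be the covariance of the two changes within a group. With equal groups and no group term, and leaving baseline adjustment aside, the pooled covariance is c + ¼ × δF × δD. The slope has the same sign.

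- If δF = 0, the pooled covariance is c. The slope can be non-zero although training does nothing to fibrosis.
- If c = 0 and δD = 0, the pooled covariance is 0. The slope is zero however much training changes fibrosis.

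**Why the list matters for error rates (illustration).** With unadjusted tests at 0.05, assumed independent, the chance of at least one false positive is 1 − 0.95⁴ = 0.185 for four primaries and 1 − 0.95⁵ = 0.226 for five.

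**The case against.** The strongest reply is that the tiers differ by level: Statistical Analyses labels its primaries by aim, so strength and muscle mass could be primary for Aim 2 and secondary for the trial as a whole. That is a natural reading, although the document does not state it, and these two outcomes are the weakest part of the conflict. It does not explain functional performance, which is primary under Aim 1 and absent from a Design primary list worded as complete. Nor does it explain the biomarkers.

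It can also be said that the power statement shows a fibrosis comparison was intended. It does, so for fibrosis the defect is an intended comparison with no model written for it. Cardiac stress has no such support.

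The regressions are presented as tests of association, which suits the stated hypothesis, and leaving out group is not in itself an error there. The point is only that they do not replace the missing comparison.

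Finally, the lead hypothesis concerns fitness, diastolic function and inflammation. Fitness has a specified comparison, as does diastolic function. This limits the damage to the tier labels and the biomarker outcomes, but the Design does call those biomarkers primary.

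**Conclusion.** The concern holds in both parts. The document does not settle which outcomes are primary: seven are called primary somewhere and two in both places (five and two within Aim 1). Two of the four Design primaries have no randomised comparison. Of these, fibrosis is covered by the claim of at least 80% power, and cardiac stress has neither a power basis nor any analysis.

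Two matching assumptions underlie the counts: that cardiac function means diastolic function, and that muscle mass belongs to DXA body composition. Dropping either, or counting the biomarkers as one item, changes the tally but removes neither the conflict nor the omission.

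The title block gives a registration date of 3/27/2014, while the attrition sentence in Power Analyses cites a 2018 publication, so this text was written or revised years after registration. That does not show that any tier changed. It does mean that the tiers declared earlier have to be checked, and they are not in this document.

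**What to change.** 1. Put one outcome list, with tiers, in both Design and Statistical Analyses. Reconcile it to the tiers declared before results were seen, which the sponsor must supply, and disclose any later change of tier. If strength and muscle mass are primary for Aim 2 only, say so. Give functional performance a tier in the Design.
2. Add the fibrosis and cardiac-stress biomarkers, each marker named, to the existing baseline-adjusted comparison of 16-week change between groups. Keep the regressions as analyses of association.
3. Name the inflammation biomarkers among the outcomes analysed the same way, at their stated tier. The Design makes them secondary and Power Analyses covers them as cytokines, but neither between-group list includes them.
4. The consent statement is in the past tense, so enrolment may already have taken place. State when each added comparison was specified, and label as post hoc any that was added after results were seen.

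The cost is small. These biomarkers are already declared outcomes, so no new measurements are needed. The number of extra comparisons depends on how many markers there are, which the document does not say. Because no multiplicity rule is stated, the tier of each comparison should be fixed in the same edit. The sponsor must retrieve the earlier tiers, and some outcomes may lose the primary label.

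### The Design and Statistical Analyses sections name different primary outcomes, and no lead outcome, testing order, multiplicity control or success rule is stated

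*Combined protocol and SAP*

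**What the plan says.** Two lists of primary outcomes stand as current text.

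- Protocol Overview, Design: "Primary outcomes are cardiorespiratory fitness, cardiac function, and biomarkers of myocardial fibrosis and cardiac stress". The next sentence begins "Secondary outcomes include muscle strength, body composition measured by Dual-energy X-ray absorptiometry (DXA" and goes on to markers of systemic inflammation.
- SAP, Statistical Analyses: change at 16 weeks, adjusted for baseline, is compared between groups for "the following primary outcomes, AIM 1: (1) functional performance, (2) aerobic capacity, (3) diastolic function; AIM 2: (1) strength, (2) muscle mass". Its secondary list is intramuscular fat, then "percent body fat, plasma glucose, insulin, and lipids, blood pressure".

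Myocardial fibrosis appears in the Statistical Analyses section only in a regression of "change in diastolic function with change in myocardial fibrosis", and those regressions leave out treatment group. Cardiac stress does not appear there.

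The only significance level is in Power Analyses, where "22 participants per group provides at least 80% power to detect a between group difference with a two-sided alpha of 0.05" is stated for each of several outcomes: diastolic function, cytokines, fibrosis biomarkers, VO₂peak and strength.

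**The concern.** A primary outcome list fixes in advance what the trial will be judged on. Here an outcome's status depends on the section read, and two kinds of biomarker called primary have no specified treatment comparison. Functional performance, muscle mass and the cardiac-stress biomarkers are each primary in one place or the other, yet are not named in the power paragraph.

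With no success rule, it is also unclear how many significant results, and which ones, would make the trial or either aim positive. If any one would do, the overall conclusion does not carry a 5% error rate. Outcome status could also be settled after the results are known.

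**Working it through.** **Step 1. The lists side by side.**

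| Outcome | Design paragraph | Statistical Analyses | Named in Power Analyses |
|---|---|---|---|
| Fitness / aerobic capacity (VO₂peak) | primary | primary | yes |
| Cardiac / diastolic function | primary | primary | yes |
| Strength | secondary | primary | yes |
| Muscle mass | secondary, if read as DXA body composition | primary | no |
| Functional performance | not listed | primary | no |
| Fibrosis biomarkers | primary | change-on-change regression only | yes |
| Cardiac-stress biomarkers | primary | absent | no |

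**Step 2. The plan's own figure.** The 22 per group cannot be reproduced, because no mean differences or SDs are given. Solving backwards for 80% power at two-sided 0.05 gives a standardized difference of (1.960 + 0.842) × √(2/22) = 0.845 by the normal approximation, or 0.865 by the t-test. So 22 is possible but cannot be verified. The documents state no familywise error rate.

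**Step 3. Chance of at least one false claim.** Conditions: *k* outcomes, each tested at two-sided 0.05; any one may be claimed; no true effect on any. The documents give no correlations, so a common correlation ρ from 0 to 0.9 is assumed.

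- Independent outcomes: 1 − 0.95^k. For example, 1 − 0.95⁵ = 0.226.
- Correlated outcomes: 1 − ∫ φ(u) [Φ((c − √ρ·u)/√(1−ρ)) − Φ((−c − √ρ·u)/√(1−ρ))]^k du, with c = 1.96.

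| Family | k | ρ = 0 | 0.5 | 0.7 | 0.9 |
|---|---|---|---|---|---|
| Aim 2 alone | 2 | 9.8% | 9.1% | 8.3% | 7.0% |
| Aim 1 alone, or Design list counted as three | 3 | 14.3% | 12.5% | 10.9% | 8.4% |
| Design list counted as four | 4 | 18.5% | 15.6% | 13.0% | 9.4% |
| All five in Statistical Analyses | 5 | 22.6% | 18.3% | 14.8% | 10.2% |
| Both lists combined | 7 | 30.2% | 23.0% | 17.8% | 11.4% |

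Simulated two-sample t-tests with 22 per group agree to within about half a percentage point.

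**Step 4. Partial null.** Suppose VO₂peak, diastolic function and strength truly improve. Of the SAP's five, only functional performance and muscle mass can then give a false claim. That is the k = 2 row: 9.8% down to 7.0%.

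**Step 5. Power cost of control.** Take an outcome with exactly 80% power at 0.05 (0.865 SD, 22 per group, no baseline adjustment). Power is 70.5% at 0.05/2 = 0.025 and 57.1% at 0.05/5 = 0.01. With two lead outcomes both at that effect, Holm gives an average power per outcome of 77% at ρ = 0, falling to 75% at ρ = 0.9. If only one of the two is real, Holm power for it is about 71%.

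**The case against.** The strongest reply is that the inflation rests on a rule the plan does not contain. The SAP groups outcomes under two aims, which is compatible with each result supporting only its own claim; on that reading, or if all outcomes had to succeed, there is no inflation. That stands as a limit on the percentages. It does not rescue the plan, because neither rule is written.

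Second, the inputs are soft. Independence sits poorly with a hypothesis in which "high-intensity exercise training will increase cardiorespiratory fitness, which will be mediated by improved diastolic function", and nothing supports a uniform 0.9. The number of tests is also uncertain: the Design text says biomarkers in the plural, and 1-RM covers six exercises. This is fair, and it means that 23% is not a ceiling. The 7% end belongs to Aim 2 alone; whole lists (k = 3 to 5) give 8.4% to 22.6%. Every value shown still exceeds 5%.

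Third, a full null is at odds with a plan that bases its power on earlier exercise trials. The partial-null calculation meets this, at 7% to 10%.

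Fourth, strength is the only outcome explicitly labelled both ways. Muscle mass conflicts only if it is part of body composition, and the other mismatches are omissions from one list. Power Analyses does contemplate a between-group difference for fibrosis biomarkers. All true, but it leaves fibrosis without an analysis model and cardiac stress without any comparison.

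Finally, the remedy may be late, since consent is reported in the past tense. The documents do not say whether outcomes have been examined by group, so the fix covers both cases.

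**Conclusion.** The concern holds. The conflict between the lists and the absence of any error-control or success rule are plain in the text and need no assumption: the primary analysis cannot be carried out as written without choosing between the lists.

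The error rate is conditional. If any one primary may be claimed at two-sided 0.05 with no true effects, it runs from about 7% (Aim 2 alone, correlation 0.9) to about 23% (all five SAP outcomes, correlation 0), depending on the family and on correlations that are assumed. No power shortfall is shown; the power figures above only price the remedy.

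**What to change.** Reconcile the two lists into one primary set, and state where and how the fibrosis and cardiac-stress biomarkers are compared between groups. Then fix one rule in a dated SAP version before outcomes are examined by group.

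- **Option A, the simplest.** A single primary at two-sided 0.05, with the rest secondary or tested in a stated fixed order. VO₂peak is the natural candidate: it leads the hypothesis, is in the power paragraph, and is on both lists if aerobic capacity and cardiorespiratory fitness are read as VO₂peak. Functional performance is the alternative: the SAP lists it first, and the Background seeks a program that "will prevent and improve disability". But it is not on the Design list or in the power paragraph. The choice is the sponsor's. Cost: fewer confirmatory claims, and in a single fixed order Aim 2 would depend on Aim 1.
- **Option B, if each aim keeps its own primary.** One lead outcome per aim, with Holm or 0.025 each, so that Aim 2 does not depend on Aim 1. Restate power at the alpha used. Cost: an outcome at exactly 80% falls to about 71% at 0.025, or to an average of 75–77% under Holm if both leads have that effect. Keeping all five as separately claimable primaries at 0.01 would leave about 57%. The plan claims at least 80% and adjusts for baseline, so these figures are illustrative.

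Neither option needs extra patients or procedures. If outcomes have already been seen by group, the change no longer protects the error rate. In that case say so, report every outcome with unadjusted p-values, and do not present a lead chosen afterwards as pre-specified.

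### Between-group models leave out the blocking factors; if those factors predict 16-week change in both arms, the test is conservative and available power goes unused

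*Combined protocol and SAP*

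**What the plan says.** Under Statistical Analyses, the dependent variable is change from baseline to 16 weeks, in "models adjusted for the baseline value of the outcome measure and treatment group". The plan does not expect to have to "adjust for sex, history of AIDS, or length of HIV infection (CD4 cell count) as our group assignment will be blocked on these factors".

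The context is confounding: "Groups will be compared at baseline for differences in potential confounders such as age and comorbidity", and further covariates enter only if the arms turn out unbalanced on something that is also related to outcome. Blocking is meant to prevent such imbalance, so this rule would not normally bring the blocking factors in. The wording does not forbid including them, but by default they are left out.

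The same approach extends beyond the primary outcomes: "Similar analyses will be performed for secondary outcomes". On dropout the plan says "Analyses will include subjects who drop out before completion of the 16-week study period by way of multiple imputation", without listing the variables in the imputation model. Under Power Analyses, "a sample size of 22 participants per group provides at least 80% power", at a "two-sided alpha of 0.05", with an allowance for 30% attrition.

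**The concern.** Blocking answers one question (will the arms be balanced on these factors?) and the plan uses that answer for another (should the model contain them?). If a blocking factor predicts change in both arms, balancing on it takes its variation out of the true sampling variance of the group difference. A model without the factor leaves that variation in the residual, so the reported standard error is larger than the true one. The actual type I error falls below 5%, and the precision gained by blocking is not turned into power.

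What is at stake is efficiency, not validity. With 22 per group and one model form for all primary and secondary outcomes, a few points of power at no cost in patients are worth having.

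**Working it through.** **1. The plan's own figure.** Power Analyses gives no effect size or SD, so 22 per group cannot be reproduced, only inverted. With two-sided alpha 0.05 and 80% power:

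- Normal approximation: d = (1.960 + 0.842) × √(2/22) = 0.845.
- Noncentral t: d = 0.865, used below.

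**2. The mechanism with perfectly balanced strata.** Set the SD of change, given the baseline value, to 1. Let R² be the share of that variance explained by the blocking factors, equally in both arms. The true variance of the group difference is 2(1 − R²)/22, while the model without the factors reports about 2/22. Reported over true standard error is therefore 1/√(1 − R²), which is 1.05, 1.12 and 1.20 at R² = 0.1, 0.2 and 0.3. Power omitting vs including the factors is 81.4 vs 83.8%, 82.9 vs 87.8% and 84.5 vs 91.6%.

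**3. Simulation with realistic blocks.** Assumptions, none of them in the documents: three binary factors with prevalences 0.15, 0.4 and 0.5 and equal effects, permuted blocks of 4 within strata, and 44 analysed. The baseline value is always in the model; 10,000 replicates. The shift per factor is √(R²/Σp(1 − p)), with Σp(1 − p) = 0.1275 + 0.24 + 0.25 = 0.6175.

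| R² | Shift per factor (SD) | Type I error, omitted / included (%) | Power, omitted / included (%) | Gain (points) |
|---|---|---|---|---|
| 0 | 0 | 5.2 / 5.0 | 78.5 / 77.4 | −1.1 |
| 0.05 | 0.28 | 4.7 / 4.9 | 79.8 / 80.3 | +0.5 |
| 0.10 | 0.40 | 4.4 / 5.4 | 79.1 / 81.1 | +2.0 |
| 0.20 | 0.57 | 3.5 / 5.3 | 80.1 / 85.8 | +5.7 |
| 0.30 | 0.70 | 2.5 / 4.9 | 82.2 / 90.5 | +8.3 |

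With the factors omitted, reported vs true standard errors at R² = 0.1, 0.2 and 0.3 were 0.305 vs 0.296, 0.304 vs 0.283 and 0.305 vs 0.267.

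**4. Other patterns of effect, 44 analysed.** Power omitted / included (%), for shifts of 0.40, 0.57 and 0.70 SD:

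| Pattern | 0.40 | 0.57 | 0.70 |
|---|---|---|---|
| Half as strong in usual care | 80.8 / 81.6 | 82.9 / 85.1 | 84.7 / 89.0 |
| Exercise arm only (residual SD 1) | 76.7 / 76.1 | 75.5 / 75.5 | 74.4 / 74.5 |

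If a single factor (prevalence 0.4) carries all of R² = 0.1, 0.2 or 0.3, power is 79.5 vs 81.5, 80.8 vs 86.2 and 82.0 vs 90.1%. Block sizes of 2 or 6, or other prevalences, moved the gains only to 2.3–2.5, 5.4–6.3 and 8.1–9.0 points.

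**5. With attrition and imputation.** 63 randomised (44/0.7 = 62.9), 30% of outcomes missing completely at random, 20 imputations, Rubin's rules, 5,000 replicates. The factors are in neither model or in both the imputation and analysis models.

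| R² (both arms) | Power, neither / both (%) | Gain (points) |
|---|---|---|
| 0 | 77.0 / 75.9 | −1.1 |
| 0.05 | 76.9 / 76.2 | −0.7 |
| 0.10 | 76.4 / 79.4 | +3.0 |
| 0.20 | 78.1 / 83.7 | +5.6 |
| 0.30 | 79.7 / 88.7 | +9.0 |

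A second run at R² = 0 gave 76.5 vs 74.2%, a cost of 2.3 points. With effects in the exercise arm only (0.40, 0.57, 0.70 SD), power was 75.0 vs 73.2, 72.1 vs 71.4 and 71.0 vs 70.5%. Monte Carlo error is about 0.4 to 0.6 points.

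**6. Cross-check.** A separately written simulation (6,000 runs per cell, blocks of 2 or 4, two sets of prevalences) gave gains of 2–3, 5–6 and 8–9 points at R² = 0.1, 0.2 and 0.3. Type I error with the factors omitted was 3.1–3.5% at R² = 0.2 and 2.1–2.6% at 0.3. Under simple randomisation it was 4.7% at R² = 0.2, so the conservatism comes from the blocking.

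**The case against.** The strongest reply is that nothing here is wrong. The trial stays valid, the power statement holds, and the plan leaves room to adjust. That stands, and it limits the point to an improvement.

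The gain also depends on an R² that the documents do not supply, for variance in change beyond a baseline value that may already carry much of what sex contributes (to strength, for example). R² of 0.2 to 0.3 needs each of three factors to shift change by 0.57 to 0.70 SD, or one factor alone by 0.91 to 1.12 SD. The latter exceeds the assumed exercise effect of 0.865 SD. The larger gains may therefore be out of reach, and with imputation the break-even lies between R² of 0.05 and 0.10. This stands too.

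Third, 80% is a floor for several outcomes, and the gain shrinks where power is higher. At assumed differences of 1.0 and 1.15 (about 90% and 96% power), the gains are 1.5, 3.4 and 4.8 points, and 0.4, 1.6 and 1.8 points. So 2, 6 and 8 points describe outcomes near the 80% floor.

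None of this makes blocking a reason to omit the factors. The possible loss is about 1 to 2 points, the possible gain is larger, and analysing by the factors used in the randomisation settles the choice before the data are seen.

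**Conclusion.** The concern holds as a cheap improvement, not an error. If the blocking factors predict 16-week change in both arms beyond the baseline value, the planned test is conservative: type I error is about 4.4%, 3.5% and 2.5% at R² of 0.1, 0.2 and 0.3. Including them then gains about 2, 6 and 8 points of power for an outcome powered at 80%, or about 1, 2 and 4 points if the same shifts are half as large in usual care. There is no material gain at R² of about 0.05 or less, or if the factors only modify response in the exercise arm.

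The direction follows from the design. The size rests on assumed R², prevalences, block size and binary coding, and on a standardised difference of 0.865 inferred from the stated sample size.

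**What to change.** Replace the sentence that sets the blocking factors aside with one that pre-specifies them, coded as in the randomisation, as main effects in every between-group model and in the imputation model, whatever the observed balance. State the coding. The plan names infection duration and CD4 count as if they were one factor and gives no categories, so the term cannot be pre-specified until that is settled. Main effects are the economical form, since three binary factors make 8 strata for 44 participants.

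The cost is SAP wording and a few degrees of freedom (3 if each factor has two levels). If no factor is prognostic, it is about 1 point of power with 44 analysed and about 1 to 2 points with 63 randomised and imputation. If the factors act only in the exercise arm, power changes by roughly −1 to +0.4 points with 44 analysed, and falls by about 0.5 to 2 points with imputation.
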